# **3.** Assessments of parent practice and feedback from families - treatment group only (see appendices for examples)

*i)* A simple therapist rating (5 point scale) on whether the parent understood the PECS stage and process and practiced the intervention will be used after each session to assess the parent's delivery of PECS in the home.

*ii) A parent-completed Social Validity Questionnaire*  has been provided by [name] of Ohio State University. It will provide feedback on families' experience of participation in the study (e.g. time demands, use of the equipment, relevance of treatment; ease of following the programme). This information will be further supplemented by qualitative data from end-of-treatment interviews conducted by an independent member of the study who will be supervised by [name] (Study co-investigator). An invitation letter will be send to parents in the intervention group and the interviews will be conducted over the phone with randomly selected parents (12 -15 interviews in total, depending on when data saturation is reached). All interviews will be recorded on an audio device and further transcribed for analysis. Each interview will last between 20-45 min and an interview

guide will be used. All data collected from the interviews will be anonymised and kept secure and confidential.

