# 5. METHODS

## 5.1 STUDY AIMS AND DESIGN:

This Feasibility and pilot randomised controlled trial (RCT) aims to:

- a) Evaluate the feasibility and acceptability of teaching the use of PECS to parents and young autistic children at home
- b) Test the feasibility of using Early Years and special school education services to recruit young children with autism in the London area
- c) Pilot and assess the use of an App designed to enable parents accurately and easily to count and rate their child's spontaneous requesting in the home context
- d) Test the feasibility and acceptability of using small body cameras (worn by the child) to gather direct observational data on communication behaviours at home.

- e) Provide pilot data, including estimates of retention rate, assessment completion and effect size, in order to prepare an application for a large multi-site RCT of home-based PECS training for parents of non-verbal young children with autism in the UK.
- f) Conduct a short term follow-up, 4 weeks after the cessation of training, to monitor the continuing use of PECS at home and any sustained progress made by the child.

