- c) Use an App provided by the research team (i.e. Tally tracker App) on their mobile phones in order to record the number and type of requests that their child makes over two specified periods as follows: 1) for 2-3 hours on a weekday after school and 2) for 2-3 hours at a weekend. This data will be collected at three time points during the duration of the study (i.e. pre and post treatment and follow-up) for both groups (i.e. TAU and treatment groups). The researcher will provide the app and assist all participants in downloading it on their mobile phones. The app is easy to use and does not involve complex features.
- d) Attach a small video camera (approximately 4cm x 2cm) similar to that used by cyclists and provided by the study team, to their child's clothing to provide direct observations about the frequency and type of spontaneous communication used by the child at home.

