#### 6. Summary of assessment measures

The following table summarises the measures to be used at baseline, end of treatment and at short term follow-up:

Descriptive measures (baseline only)	Pre and post treatment measures	Post treatment only	Follow-up*
Social Communication Questionnaire	PECS usage (telephone App and video)	Assessment of parent treatment fidelity*	PECS usage* (telephone App and video)
Mullen Scales of Development	Communication Development Inventory (CDI)	Feedback on participation using Social Validity Questionnaire*	
Adaptive Behaviour Assessment System (ABAS)		Child and Adolescent Service Use Schedule (CA- SUS)	

\* treatment group only

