## 8. STUDY OUTCOMES

As this study is designed as a feasibility study primary outcome data will focus on the following variables:

- a) Successful recruitment strategy i.e. recruitment of 64 eligible participants
- b) Data collection on questionnaire and direct assessments for all participants at each assessment time point
- c) Utility of the App and body-worn cameras and quality of data obtained from this equipment.
- d) Retention of families in both groups,
- e) Number of home-based sessions delivered by the therapist
- f) Evaluation of the PECS stages established for treatment families (parent treatment fidelity)
- g) Child and Adolescent Service Use Schedule (CA-SUS) to ascertain local provision
- h) Parent, teacher, research assistant and therapist feedback on feasibility and acceptability (Social Validity Questionnaire, focus groups).

The secondary outcome data will focus on the following:

a) PECS usage - (telephone App and video). The RA will extract frequency counts from the App and score episodes of requesting from films (remaining blind to group allocation).

Experience of coding behaviour from video suggests that it should be possible to scroll through the video at a medium-fast forward pace to identify episodes of requesting behaviour and then to score them according to 2 codes: 1) use of PECS, 2) other forms of request (e.g. speech, vocalisations or gestures etc.)

b) Communication Development Inventory (CDI) to explore whether there has been any overall change in children's communication skills.

Additional outcome data:

a) A short anonymous questionnaire to explore children's access to PECS intervention from professionals working with children with autism. The questionnaire will be circulated through professional Clinical Excellent Networks (CENs) via Survey Monkey. It is designed to take under 10 minutes to complete, consisting mainly of multiple choice questions.

b) A short anonymous questionnaire to ascertain if individuals transferring to adult services do so with some skills using PECS and also to establish if PECS is included in treatment for adults. The questionnaire will be sent through professional Clinical Excellence Networks (CENs) to professionals working in adult therapy services via Survey Monkey. It takes under 10 minutes to complete and is mainly comprised of multiple choice questions.

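### Parents' views on the App, the camera and the time demands are sought in the treatment group only, although both arms use the equipment

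*Protocol*

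**What the plan says.** The restriction appears in three places in the protocol, and they agree.

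- The feedback section is headed "Assessments of parent practice and feedback from families - treatment group only".
- Within it, the interview text reads "An invitation letter will be send to parents in the intervention group". Between 12 and 15 interviews are planned, depending on saturation.
- In the Summary of assessment measures, the entry "Feedback on participation using Social Validity Questionnaire" carries an asterisk, and the asterisk means treatment group only.

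The questionnaire is not confined to treatment. Its stated content includes "time demands, use of the equipment, relevance of treatment; ease of following the programme".

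The equipment, by contrast, is used in both arms. Section 6.2 has App data collected "for both groups (i.e. TAU and treatment groups". In the summary table the pre- and post-treatment entry for App and video has no asterisk; only the follow-up entry does.

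The aims follow the equipment, not the arm. Aim (d) in section 5.1 is to "Test the feasibility and acceptability of using small body cameras (worn by the child", and aim (c) is to pilot the App as an accurate and easy tool for parents. Neither names an arm. In section 8, primary outcome (c), on the usefulness of the equipment and the quality of its data, is also unrestricted, and outcome (d) is "Retention of families in both groups".

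**The concern.** The questionnaire mixes two kinds of item. Whether the treatment was relevant and the programme easy to follow can be asked only of parents who received it. How much time the study took, and how the equipment was to use, can be asked of every parent. The restriction suits the first kind and has been applied to both.

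The pilot is meant to prepare a large multi-site trial (aim e), and section 9 plans an analysis of the App and video request counts by intention to treat. Control families in that trial would have to do the same recording as treated families. Whether they find it tolerable is therefore a design question for that trial, and the tools described here do not put it to control parents.

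**Working it through.** No figure in the protocol rests on this point. The only calculated figure, the power statement in section 9, reproduces. With 32 × 0.9 = 28.8 per arm and power = Φ(d√(n/2) − 1.96), d = 0.5 gives Φ(1.897 − 1.960) = 47.5% and d = 0.6 gives Φ(2.277 − 1.960) = 62.4%, against the stated 47% and 62%. It has no bearing on what follows.

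**Step 1: who uses the equipment and who is asked about it.**

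| Item | Treatment | TAU | Source (Protocol) |
|---|---|---|---|
| App, pre and post | yes | yes | 6.2 (c); Summary of assessment measures |
| Camera, pre and post | yes | yes | Summary of assessment measures (no asterisk) |
| Social Validity Questionnaire | yes | no | Feedback section; Summary of assessment measures (asterisk) |
| Interviews | yes | no | Feedback section |
| Assessment completion, data quality, retention | yes | yes | Section 8 (b) to (d) |
| Focus groups | not stated | not stated | Section 8 (h) |

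Section 6.2 (c) places App follow-up in both groups, while the short-term follow-up section and the table limit follow-up to the treatment group. That does not matter here: on either version both arms record before and after treatment.

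**Step 2: coverage.** Section 5.3 allocates 32 families to each group, 64 in all. Families using the equipment: 64. Families offered the questionnaire or eligible for interview: 32. Coverage is 32/64 = 50%.

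**Step 3: what adding TAU parents gains.** The approximate 95% half-width for a proportion is 1.96 × √(p(1 − p)/n). The values of p are assumptions; the protocol gives none.

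| Families | p = 50% | p = 80% |
|---|---|---|
| 32 (treatment only) | ±17.3 points | ±13.9 points |
| 64 (both arms) | ±12.2 points | ±9.8 points |
| 29 (treatment only, after 10% loss) | ±18.2 points | ±14.6 points |
| 58 (both arms, after 10% loss) | ±12.9 points | ±10.3 points |

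The pooled gain is moderate. The larger gain is that a TAU estimate exists at all, with the precision of the 32-family row. A comparison of arms would be weak: at p = 50% in each, the half-width for the difference is 1.96 × √(2 × 0.25/32) = ±24.5 points. Reporting by arm should therefore be descriptive.

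**The case against.** The restriction is deliberate and stated consistently, and a questionnaire that asks about treatment is reasonably given to treated parents. That stands for the treatment items, for aim (a) and for the therapist's fidelity rating. It does not reach the equipment and time-demand items.

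Several stronger readings are tempting, and the protocol does not support them.

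- **That acceptability goes unmeasured in TAU.** Section 8 (b) to (d) provides behavioural evidence in both arms: whether families complete, whether the recordings are usable, whether they stay. Section 8 (h) adds research assistant feedback and focus groups with no arm named. Since attendance at the focus groups is nowhere described, TAU parents are neither included nor excluded. The gap is in parents' stated views.
- **That the treatment-arm answer is biased upwards.** Therapist contact could make parents more favourable. But treated families also carry up to 12 home sessions (section 7) and, under the follow-up section and the table, an extra recording round. Their ratings of time demands could be worse.
- **That TAU feedback would explain differential loss.** A post-treatment form reaches mainly families still in the study, so it says little about those who left.
- **That acceptability of allocation to TAU should have been measured.** It is not among the aims in section 5.1.
- **That some interviews should go to TAU families.** The interview sample is tied to saturation among treated parents, so moving interviews is a trade-off and the point does not require it.

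**Conclusion.** The point holds as a gap in coverage. The only parent-reported measures of equipment use and time demands that the protocol describes are confined to 32 of 64 families, while aims (c) and (d) and primary outcome (c) concern equipment used by all 64. For TAU families, completion, data quality and retention show whether they managed the recording, but not how they found it. The difference between the arms' views could go either way, and its size is unknown.

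This rests on the planned allocation and on reading the unmarked pre- and post-treatment table entry as covering both arms, which section 6.2 confirms for the App. The numbers in practice will be smaller. Appendix 15.1 records 33 families at the April 2020 pause, and Appendix 15.2 closes recruitment on 12/01/2021 without a final count. On an equal split, which is an assumption, 33 families would mean about 16 unasked. The share, about half, does not depend on the total. This is an inexpensive improvement; it does not undermine the trial.

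**What to change.** - Give TAU parents the equipment and time-demand items of the Social Validity Questionnaire, omitting the treatment items, at the post-treatment assessment, where the table already has them completing the CDI and CA-SUS.
- Amend the heading of the feedback section, and remove the asterisk in the Summary of assessment measures for those items only.
- Report App and camera acceptability by arm, descriptively.
- Have an unblinded team member send and collect the forms, since a form without treatment items reveals the allocation. Section 5.4 already provides an unblinded contact after randomisation, so the research assistant can stay blind.
- State in section 8 (h) who attends the focus groups.

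The cost is one short form per TAU family, 32 at the planned size, with no change to sample size or power. For families already past their post-treatment assessment, such as those in School 1 in Appendix 15.1, there is no remaining post-treatment contact to use. They would need a separate retrospective request, or the report should say that their views were not sought.

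### Parent-reported acceptability is scheduled only after treatment, with no stated route for families who withdraw and no assurance that early stoppers are interviewed

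*Protocol*

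**What the plan says.** Section 5.1 makes the acceptability of home PECS teaching aim (a). Section 8 lists it as primary outcome (h), drawn from parents, teachers, the research assistant and the therapist.

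The parents' part is described under Assessments of parent practice and feedback from families, item ii:

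- **Questionnaire.** The Social Validity Questionnaire covers, for example, "time demands, use of the equipment, relevance of treatment; ease of following the programme". In the summary table of measures, "Feedback on participation using Social Validity Questionnaire" appears once, in the post-treatment-only column, and is marked for the treatment group only.
- **Interviews.** The questionnaire is "supplemented by qualitative data from end-of-treatment interviews". On the frame: "An invitation letter will be send to parents in the intervention group". On selection: "the interviews will be conducted over the phone with randomly selected parents (12 -15 interviews in total, depending on when data saturation is reached").

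Section 7 sets 12 sessions over 18 weeks. Section 5.4 lets parents withdraw at any point in the project. Section 8 counts "Retention of families in both groups" as outcome (d) and the number of home sessions delivered as outcome (e). The protocol mentions neither feedback at withdrawal nor a recorded reason for stopping.

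**The concern.** Families who find a home programme hard to sustain are the ones whose view a feasibility study most needs, and they may be gone when the questions are asked. Both dated parent instruments fall after an 18-week programme. If leavers are less satisfied than stayers, the acceptability result is biased upwards.

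The reason for leaving is lost as well. Outcomes (d) and (e) would tell the designers of a full trial how many families stopped and after how many sessions. They would not show whether the cause was the number of visits, the App, the camera, the child's response or something unrelated, and each would call for a different change.

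**Working it through.** **1. The protocol's own figure.** Section 9 gives 47% power at effect size 0.5 and 62% at 0.6, with a 10% loss. With 32 × 0.9 = 28.8 per arm, two-sided 0.05 and the normal approximation, power = Φ(d·√(n/2) − 1.96):

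- d = 0.5: Φ(1.897 − 1.960) = 47.5%
- d = 0.6: Φ(2.277 − 1.960) = 62.4%

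Both reproduce. The figure matters here only because it fixes the planned loss at 32 − 28.8 = 3.2, or about 3 families per arm. That 10% covers equipment faults as well as drop-out, so 3 is an upper reading of the families it implies will leave.

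**2. Which families the instruments reach.**

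| Family | Questionnaire | Interview |
|---|---|---|
| Completes the sessions | Due post treatment | In the frame |
| Stops sessions, stays in the study | Still due post treatment | In the frame, reached only by chance |
| Withdraws from the study | No stated route | Not excluded by the invitation wording, but not provided for |

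**3. Chance that the interviews miss every early stopper.** Suppose all 32 PECS families are in the frame, s have stopped, and k are drawn at random. Then P(none) = C(32 − s, k) / C(32, k). For s = 3:

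- k = 12: (20 × 19 × 18) / (32 × 31 × 30) = 6840 / 29760 = 23%; expected number heard 12 × 3/32 = 1.1
- k = 15: (17 × 16 × 15) / 29760 = 4080 / 29760 = 14%; expected number heard 15 × 3/32 = 1.4

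The documents give no other count of stoppers. As assumed alternatives, s = 2 gives 38% (k = 12) and 27% (k = 15), and s = 6 gives 4% and 1%.

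**4. Possible size of the bias in the questionnaire.** The satisfaction counts are illustrative, and leavers are taken as not answering.

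- 3 leavers: 27 of 29 respondents satisfied reads as 93%. Over all 32 the value lies between 27/32 = 84% (no leaver satisfied) and 30/32 = 94% (all satisfied).
- 6 leavers (an assumed loss of about 20%, not in the documents): 24 of 26 reads as 92%. The range over all 32 is 24/32 = 75% to 30/32 = 94%.

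**5. A smaller sample.** Section 15.1 reports 33 families at the April 2020 pause, and Section 15.2 reports that recruitment closed on 12/01/2021. The final number is not given. If the PECS arm held 16 families and 2 stopped, 12 random interviews would miss both with probability (4 × 3)/(16 × 15) = 5%, and 15 interviews could not miss both. The interview gap then shrinks, while the questionnaire gap for families who withdraw stays.

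**The case against.** The strongest reply is that stopping sessions is not the same as leaving the study. Primary outcome (b) seeks data from all participants at every assessment point, and Section 9 analyses request counts by intention to treat. A family that gives up sessions but stays in the study is still due the questionnaire. This stands, and it narrows the questionnaire gap to families who withdraw.

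Three stronger readings are tempting, and the protocol supports none of them.

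- **Acceptability comes from completers only.** The interview invitation goes to the intervention group with no such limit. A random draw from all 32 would include at least one of three stoppers with probability 77% to 86%. Randomness does not itself cause bias; it only fails to secure coverage.
- **There is no other channel.** Outcome (h) also takes teacher, research assistant and therapist feedback and focus groups, and the therapist sees the family at each session. No timing is given for these sources, and staff feedback is not the parent's own account. The therapist's per-session scale rates the parent's understanding and practice.
- **The background section shows an unmonitored harm of PECS.** Section 4 links emotional and behavioural problems to the lack of communication, and reports a possible reduction in problem behaviours with PECS.

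Two further points are fair. The questionnaire items and interview guide are not in the text reviewed, so they may ask about reasons; that would not change when they are used. Random selection also keeps the team from hand-picking interviewees, so replacing it altogether would be partly a matter of preference.

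**Conclusion.** The point holds in limited form. The plan fixes both dated parent instruments after treatment, states no route for families who withdraw, and leaves it to chance whether early stoppers are interviewed. Parent-reported acceptability can be biased upwards, and the reasons for stopping go unrecorded by any measure the protocol describes.

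At the planned size with 3 stoppers in the frame, the interviews miss all of them with probability 14% to 23%. In the worst case, a reported 93% would stand for 84% of allocated families. These figures assume that all of the 10% loss is families leaving, that no leaver answers the questionnaire and, for the worst case, that every leaver is dissatisfied. The documents give no data on why families stop, so the direction of the bias is a reasonable expectation and not an established fact. Early stopping remains visible in outcomes (d) and (e). This is worth correcting, but it does not undermine the study.

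**What to change.** - Offer the Social Validity Questionnaire at the end of treatment or when a family stops, whichever comes first.
- Add one optional reason-for-stopping item in both arms. Treatment-as-usual families also use the App and camera, so their reasons matter too, and withdrawal must stay free of any duty to explain.
- Within the same 12-15 interviews, invite families who stopped early first and choose the rest at random.
- Report acceptability with all families allocated to PECS as the denominator, showing non-responders separately.

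The cost is a change of timing for an existing questionnaire, one extra item and a different order of invitation, with no added visit or interview. Some leavers will decline, and the interview sample is no longer a simple random one, which the report should say. Where families have already finished, the change of denominator can still be made at reporting, and the rest can carry over to the full trial.

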## 4. Other provision/interventions currently received.

The Child and Adolescent Service Use Schedule  (CA-SUS) completed by parents will be used to assess the types and amounts of local interventions utilised by families (e.g. speech and language therapy, alternative medicines and other education provision). Staff will be asked about PECS use within the school.

## 5. Short-term follow-up (Intervention group only)

Previous studies have indicated that PECS use is not maintained once direct intervention has ceased . Thus, approximately one month post-treatment, use of PECS at home will be assessed using the App and cameras (as described above) to determine whether families have continued to use the intervention once they are no longer actively involved in therapy and to see if progress by the child has been sustained.

Table 1 summarises the measures to be used at baseline, end of treatment and at short term follow-up.

#### 6. Summary of assessment measures

The following table summarises the measures to be used at baseline, end of treatment and at short term follow-up:

Descriptive measures (baseline only)	Pre and post treatment measures	Post treatment only	Follow-up*
Social Communication Questionnaire	PECS usage (telephone App and video)	Assessment of parent treatment fidelity*	PECS usage* (telephone App and video)
Mullen Scales of Development	Communication Development Inventory (CDI)	Feedback on participation using Social Validity Questionnaire*	
Adaptive Behaviour Assessment System (ABAS)		Child and Adolescent Service Use Schedule (CA- SUS)	

\* treatment group only

